12.6.3.1.2 Missing Month Only

- The day will be treated as missing and both month and day will be replaced according to the above procedure.

12.6.3.1.3 Missing Day Only

- If the month and year of the incomplete start date are the same as the month and year of the date of the first dose of IP, then the day of the date of the first dose of IP in the SHP647-303 study will be assigned to the missing day.
- If either the year is before the year of the date of the first dose of IP or if both years are the same but the month is before the month of the date of the first dose of IP in the SHP647-303 study, then the last day of the month will be assigned to the

missing day.

- If either the year is after the year of the date of the first dose of IP or if both years are the same but the month is after the month of the date of the first dose of IP in the SHP647-303 study, then the first day of the month will be assigned to the missing day.

12.6.3.2 Incomplete Stop Date

The following rules will be applied to impute the missing numerical fields. If the date of the last dose of IP in the SHP647-303 study is missing, then replace it with the last visit date. If the imputed stop date is before the start date (imputed or non-imputed start date), then the imputed stop date will be equal to the start date.

12.6.3.2.1 Missing Day and Month

- If the year of the incomplete stop date is the same as the year as of the date of the last dose of IP, then the day and month of the date of the last dose of IP in the SHP647-303 study will be assigned to the missing fields.
- If the year of the incomplete stop date is before the year of the date of the last dose of IP in the SHP647-303 study, then 31 December will be assigned to the missing fields.
- If the year of the incomplete stop date is after the year of the date of the last dose of IP in the SHP647-303 study, then 01 January will be assigned to the missing fields.

12.6.3.2.2 Missing Month Only

- The day will be treated as missing and both month and day will be replaced according to the above procedure.

12.6.3.2.3 Missing Day Only

- If the month and year of the incomplete stop date are the same as the month and year of the date of the last dose of IP, then the day of the date of the last dose of IP in the SHP647-303 study will be assigned to the missing day.
- If either the year is before the year of the date of the last dose of IP or if both years are the same but the month is before the month of the date of the last dose of IP in the SHP647-303 study, then the last day of the month will be assigned to the missing day.
- If either the year is after the year of the last dose of IP or if both years are the same but the month is after the month of the date of the last dose of IP in the

SHP647-303 study, then the first day of the month will be assigned to the missing day.

12.6.4 Missing Date Information for Adverse Events

For AEs, the default is to only impute incomplete (ie, partially missing) start dates. If start date is missing, no imputation will be performed.

12.6.4.1 Incomplete Start Date

Follow the same rules as in Section [12.6.3.1](#).

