## **8. ADVERSE AND SERIOUS ADVERSE EVENTS ASSESSMENT**

### **8.1 Definition of Adverse Events, Period of Observation, Recording of Adverse Events**

An AE is any untoward medical occurrence in a clinical investigation subject administered a pharmaceutical product and that does not necessarily have a causal relationship with this treatment. An AE can therefore be any unfavorable and unintended sign (including an abnormal laboratory finding), symptom, or disease temporally associated with the use of a medicinal (investigational) product, whether or not related to the medicinal (investigational) product (International Council for Harmonisation [ICH] Guidance E2A 1995).

All AEs are collected from the time the informed consent and/or assent is signed until the end of the defined safety follow-up period stated in Section 7.2.3. Where possible, a diagnosis rather than a list of symptoms should be recorded. Resolved AEs considered to be significant by the investigator that occurred in induction studies SHP647-301 or SHP647-302 will be captured as part of the SHP647-303 baseline medical history, while ongoing AEs from Studies SHP647-301 or SHP647-302 will be captured as AEs in SHP647-303 and followed throughout the SHP647-303 study. If a diagnosis has not been made, then each symptom should be listed individually. All AEs should be captured in the subject's source documents. In addition to untoward AEs, unexpected benefits outside the investigational product indication should also be captured in the subject's source document.

All AEs must be followed to closure (the subject's health has returned to his/her baseline status or all variables have returned to normal), regardless of whether the subject is still participating in the study. Closure indicates that an outcome is reached, stabilization achieved (the investigator does not expect any further improvement or worsening of the event), or the event is otherwise explained. When appropriate, medical tests and examinations are performed so that resolution of event(s) can be documented.

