7.1 Adverse Events

Adverse events will be coded using MedDRA Version 19.1 2016.

Treatment-emergent AEs (TEAEs) are defined as AEs with start dates at the time of or following the first exposure to IP in the SHP647-303 study.

An overall summary of the number of subjects with TEAEs will be presented, including the number and percentage of subjects with any TEAEs, serious TEAEs, TEAEs related to IP, related serious AEs (SAEs), TEAEs leading to discontinuation of IP, TEAEs leading to study discontinuation, and TEAEs leading to death.

The number of events, incidence, and percentage of subjects reporting TEAEs will be presented by treatment group as listed in Appendix 16.6; by preferred term; by SOC and preferred term; and by SOC, preferred term, and maximum severity. Treatment-emergent AEs considered related to IP will also be summarized by SOC and preferred term. If more than one AE occurs with the same preferred term for the same subject, then the

subject will be counted only once for that preferred term using the most severe and most related occurrence for the summarization by severity and by relationship to IP.

The most common TEAEs (incidence $\geq 2\%$ in any treatment group) will be summarized by preferred term in descending frequency by treatment group as listed in Appendix 16.6.

Serious TEAEs, TEAEs leading to discontinuation of the study or study medication, and injection site AEs will be summarized by SOC, preferred term, and treatment group as defined in Appendix 16.6. Adverse events leading to withdrawal, serious AEs, and deaths will be similarly summarized or listed.

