12.6.3 Missing Date Information for Prior or Concomitant Medications (Therapies/Procedures)

The induction study (SHP647-301 or SHP647-302) imputed dates will be used for prior medications for those collected in induction study.

For prior or concomitant medications collected in SHP647-303, including rescue medications, incomplete (ie, partially missing) start date and/or stop date will be imputed. When the start date and the stop date are both incomplete for a subject, impute the start date first.

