12.6.3.1.1 Missing Day and Month

- If the year of the incomplete start date is the same as the year of the date of the first dose of IP, then the day and month of the date of the first dose of IP in the SHP647-303 study will be assigned to the missing fields.
- If the year of the incomplete start date is before the year of the date of the first dose of IP in the SHP647-303 study, then December 31 will be assigned to the missing fields.
- If the year of the incomplete start date is after the year of the date of the first dose of IP in the SHP647-303 study, then 01 January will be assigned to the missing fields.

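### An adverse event known to be ongoing from induction becomes treatment-emergent in maintenance when the known part of its partial start date matches the first SHP647-303 dose

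*SAP*

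**What the plan says.** - **Which AEs are in the data.** Protocol 8.1: "ongoing AEs from Studies SHP647-301 or SHP647-302 will be captured as AEs in SHP647-303 and followed throughout the SHP647-303 study".
- **How a TEAE is defined.** SAP 7.1: "Treatment-emergent AEs (TEAEs) are defined as AEs with start dates at the time of or following the first exposure to IP in the SHP647-303 study". Nothing excludes an event already present at entry.
- **How a partial AE start date is completed.** SAP 12.6.4.1: "Follow the same rules as in Section" 12.6.3.1. SAP 12.6.4 limits this to partial dates: "If start date is missing, no imputation will be performed".
- **What 12.6.3.1 does.** With day and month missing and the year equal to that of the first dose, "the day and month of the date of the first dose of IP in the SHP647-303 study will be assigned" (12.6.3.1.1). If the year is earlier, "then December 31 will be assigned to the missing fields". With only the day missing (12.6.3.1.3), a month and year equal to those of the first dose give the first dose date, and an earlier month gives the last day of that month. The one override is a complete stop date that falls before the imputed start.
- **What is done for medications.** SAP 12.6.3: "The induction study (SHP647-301 or SHP647-302) imputed dates will be used for prior medications for those collected in induction study". There is no counterpart for AEs.

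**The concern.** Protocol 7.2.1 puts the maintenance baseline visit on the day of the induction Week 12 visit, with the first SHP647-303 dose given after the baseline procedures. An AE documented as ongoing from induction therefore started before that dose. The order of onset and dosing is known even when the exact onset day is not. The imputation rule ignores this and can place the start on the dosing day, where the TEAE definition picks it up.

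The maintenance TEAE tables, including those by severity and by relationship, could then contain events that did not begin on maintenance treatment. There is also a knock-on effect. SAP 12.6.5 imputes a missing severity as Mild before the first dose but as Severe on or after it, and SAP 12.6.6 imputes a missing relationship as Related on or after it. A misdated record with either field missing would be escalated as well.

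**Working it through.** The plan states no figure on this point, so there is none to reproduce. The check applies the rules as written.

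**Inputs.** Imputation rules: SAP 12.6.3.1, 12.6.3.1.1 and 12.6.3.1.3. TEAE definition: SAP 7.1. Induction length: 12 weeks, or 84 days (Protocol 4.1 and 7.2.1). Assumptions not in the documents: onset is uniform over days 1 to 84 before the first SHP647-303 dose, the AE is still ongoing at that dose, and first-dose dates are spread evenly over the calendar.

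**Worked cases** (AE ongoing at the first dose):

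| First dose | True onset | Recorded as | Imputed start | TEAE? | Correct? |
|---|---|---|---|---|---|
| 20 Jun 2019 | 5 Jun 2019 | Jun 2019 | 20 Jun 2019 | Yes | No |
| 20 Jun 2019 | 10 May 2019 | May 2019 | 31 May 2019 | No | Yes |
| 20 Jun 2019 | 10 May 2019 | 2019 | 20 Jun 2019 | Yes | No |
| 10 Feb 2019 | 15 Dec 2018 | Dec 2018 or 2018 | 31 Dec 2018 | No | Yes |

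The stop-date override does not rescue the wrong rows. It acts only if the AE stopped before the imputed start, which here is the first dose date, and such an AE would not be ongoing.

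**Share misclassified, day missing.** If the first dose falls on day *d* of a month, *d* − 1 of the 84 possible onset days lie in the same month. The share is (*d* − 1)/84: 0% for *d* = 1, 9/84 = 10.7% for *d* = 10, 19/84 = 22.6% for *d* = 20, and 30/84 = 35.7% for *d* = 31. Over a 365-day year, the sum of (*d* − 1) is 7 × 465 + 4 × 435 + 378 = 5,373. The mean is 5,373/365 = 14.72, and 14.72/84 = **17.5%**.

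**Share misclassified, day and month missing.** If the first dose falls on day *D* of the year, min(*D* − 1, 84) of the 84 onset days lie in the same year. For *D* = 1 to 84 these sum to 0 + 1 + … + 83 = 3,486. The other 281 days give 281 × 84 = 23,604. The share is (3,486 + 23,604)/(365 × 84) = 27,090/30,660 = **88.4%**. Enumerating every first-dose date from 2018 to 2020 gives the same two figures.

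**Scale.** One false TEAE needs on average 1/0.175 = 5.7 carried-over records with the day missing, or 1/0.884 = 1.1 with only the year known.

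**Between arms.** SAP 7 makes the primary safety presentation by SHP647-303 treatment regardless of induction treatment (Appendix 16.6, Page 3). On the planned numbers (Protocol 9.6; 104 placebo-induction subjects split 2:2:1):
- Placebo column: 148 + 148 + 104/5 = 316.8 subjects, of whom 296/316.8 = 93% had active induction.
- Each ontamalimab dose column: 148 + 2 × 104/5 = 189.6 subjects, of whom 148/189.6 = 78% had active induction.

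The induction mix differs, so carried-over AEs need not be equally frequent across columns.

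**After the fix.** If the induction start date is kept, or capped before the first dose, the misclassified share is 0%.

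**The case against.** Assigning the first-dose date to an uncertain onset is a familiar conservative convention: it over-counts rather than hides events. That is sound when the order of onset and dosing is unknown. Here it is known, and Protocol 8.1.1 already requires worsening of a pretreatment event to be recorded as a new AE, so excluding the carried-over record loses no emergent signal.

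It can also be argued that the AE section inherits the scope of SAP 12.6.3, under which medications recorded in induction keep their induction dates. The text does not support this. SAP 12.6.4.1 cites 12.6.3.1, not 12.6.3, and the carry-over sentence names prior medications only.

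Several limits do stand. Subjects are asked about AEs at each visit (Protocol 7.3.3.4) and data are queried (Protocol 9.2), so an onset within the previous 12 weeks known only to the year should be rare. Severity and relationship are fields the investigator must complete (Protocol 8.1.1 and 8.1.2), so the escalation needs a second gap. A subject counts once per preferred term (SAP 7.1), so a false TEAE may raise the event count without changing incidence. No formal safety testing is planned (Protocol 9.5).

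A reader might infer that every partial AE start date is moved to the first dose. That is not so: an earlier month or year is imputed before the dose. Under the uniform-onset assumption about 82% of carried-over AEs with only the day missing are classified correctly (100 − 17.5 = 82.5).

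**Conclusion.** The gap is real but narrow. It affects only AEs documented as ongoing from induction whose partial start date matches the first SHP647-303 dose in year, or in month and year. For those records the stated rules give a classification that the trial's own information contradicts.

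The shares of about 17.5% (day missing) and 88% (year only) rest on uniform onset over 84 days. Onsets nearer the first dose would raise both, and older onsets would lower both. Neither document says how many carried-over AEs have partial dates, so the effect on TEAE counts cannot be sized and may be small.

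Two further inferences are tempting but unsupported. One is that the false events fall equally on both arms and pull comparisons toward no difference. The pooled primary safety columns have different induction mixes (93% against 78% active induction on planned numbers), so the direction is not established. The other is that the same event would be treatment-emergent in both the induction and the maintenance study. That depends on the induction studies' analysis rules, which are not in these documents.

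**What to change.** Add to SAP 12.6.4.1:

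> *For AEs ongoing from SHP647-301/302, use the induction study start date (observed or as imputed in that study); if it is still partial, impute no later than the day before the first SHP647-303 dose. Section 12.6.3.1 applies only to AEs with onset first reported in SHP647-303. Worsening recorded as a new AE keeps its own onset date.*

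This gives AEs the protection that SAP 12.6.3 already gives prior medications. The cost is small: a short SAP addition, one programming condition, and a link from carried-over AEs to the induction AE records. Neither document describes a flag or linkage for these AEs, so the sponsor should confirm that they can be identified. No additional subject assessments are needed.

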12.6.4.2 Incomplete Stop Date

Not applicable.

12.6.5 Missing Severity Assessment for Adverse Events

If severity is missing for an AE starting prior to the date of the first dose of IP, then a severity of “Mild” will be assigned. If the severity is missing for an AE starting on or after the date of the first dose of IP in the SHP647-303 study, then a severity of “Severe” will be assigned. The imputed values for severity assessment will be used for incidence summaries, while the actual values will be used in data listings.

12.6.6 Missing Relationship to IP for Adverse Events

If the relationship to IP is missing for an AE starting on or after the date of the first dose of IP in the SHP647-303 study, a causality of “Related” will be assigned. The imputed values for relationship to double-blind IP will be used for incidence summaries, while the actual values will be presented in data listings.

12.6.7 Character Values of Clinical Laboratory Variables

If the reported value of a clinical laboratory variable cannot be used in a statistical analysis due to, for example, that a character string is reported for a numerical variable, the appropriately determined coded value will be used in the statistical analysis. However, the actual values as reported in the database will be presented in data listings.

13. ANALYSIS SOFTWARE

Statistical analyses will be performed using Version 9.4 (or newer) of SAS® on a suitably qualified environment.

14. CHANGES TO ANALYSIS SPECIFIED IN PROTOCOL

The following changes to the analysis specified in Protocol Amendment 3 dated 17 Sep 2020 (final version 1.0 dated 10 Jul 2017, Amendment 1 dated 11 Sep 2018, Amendment 2 dated 11 Nov 2019) have been made.

Changed the other secondary endpoint total sign/symptom score calculation from sum of daily e-diary entries to average of daily e-diary entries.

16. APPENDICES

16.1 Schedule of Activities Prior to Amendment 3

Study Week	Baseline ^a	Treatment														Follow-Up ^b	
	0	4	8	12	16	20	24	28	32	36	40	44	48	52 ^c		60 ^c	68 ^c
Visit Number	1	2	3	4	5	6	7	8	9	10	11	12	13	14 (Pt 1) ^d	14 (Pt 2)	15	16
Study Day	1	28	56	84	112	140	168	196	224	252	280	308	336		364	420	476
Visit Window	None	±7 days														±7 days	±7 days
PRO-UC daily e-diary data ¹	IDT	X	X	X	X	X	X	X	X	X	X	X	X	X	X		
Health Assessment ^r																	
IBDQ	IDT			X			X								X		
██████████	IDT			X			X								X		
Hospitalizations, inpatient days, ██████████ (HRUA)	IDT	X	X	X	X	X	X	X	X	X	X	X	X		X		X
██████████	IDT			X			X								X		
██████████	IDT			X			X								X		
██████████	IDT			X			X								X		
SF-36-v.2, acute	IDT			X			X								X		
██████████	IDT														X		
Treatment Procedures																	
Randomization ^s	X																
Administration of SHP647 or placebo ^s	X	X	X	X	X	X	X	X	X	X	X	X	X				
Adverse events	X	X	X	X	X	X	X	X	X	X	X	X	X	X	X	X	X
Concomitant medication and procedures	X	X	X	X	X	X	X	X	X	X	X	X	X	X	X	X	X
Dispense stool collection kit for stool sample ^t			X			X							X				

Study Week	Baseline ^a	Treatment												Follow-Up ^b			
	0	4	8	12	16	20	24	28	32	36	40	44	48	52 ^c		60 ^c	68 ^c
Visit Number	1	2	3	4	5	6	7	8	9	10	11	12	13	14 (Pt 1) ^d	14 (Pt 2)	15	16
Study Day	1	28	56	84	112	140	168	196	224	252	280	308	336		364	420	476
Visit Window	None	± 7 days												± 7 days		± 7 days	

ADA=antidrug antibodies; β-hCG=beta-human chorionic gonadotropin; [REDACTED]; ECG=electrocardiogram; [REDACTED]; [REDACTED]; ET=early termination; FSH=follicle-stimulating hormone; HEENT=head, eyes, ears, nose, and throat; HRUA=Healthcare Resource Utilization Assessment; IBDQ=Inflammatory Bowel Disease Questionnaire; IDT=induction study (SHP647-301 or SHP647-302); LTS=long-term safety extension; [REDACTED]; NAb=neutralizing antibody; [REDACTED]; [REDACTED]; PRO=patient-reported outcomes; Pt=part; SF-36=Short Form-36 health survey; [REDACTED]; UC=ulcerative colitis; [REDACTED].
 
^a The Week 12 assessment from the induction study (SHP647-301 or SHP647-302) will be used as the baseline (Day 1/Week 0) assessments for Study SHP647-303.
 
^b No follow-up is required if subject is entering the LTS study (SHP647-304) at the Week 52 visit (Visit 14).
 
^c Any subject who prematurely withdraws from the study should return for an early termination visit and then enter into the safety follow-up period if not entering the LTS study (SHP647-304). For subjects participating in the 16-week safety follow-up period (not entering the LTS study), the Week 60 visit will routinely be conducted by telephone; however, as an exception the visit can be performed as a study site visit if preferred. The Week 68 visit will take place at the study site.
 
^d Part 1 of Visit 14 should be scheduled preferably within 5 to 7 days before Part 2; this will allow sufficient time for data from the centrally read endoscopy to be available at Part 2 of the visit.
 
^e Eligibility will be assessed after the consent form is signed and after induction study SHP647-301 or SHP647-302 Week 12, Visit 6 (Part 2) procedures are completed.
 
^f Medical history for induction study SHP647-301 or SHP647-302 will be used as the baseline medical history data for study SHP647-303.
 
^g Complete physical examination includes the review of the following body systems: general appearance, skin, HEENT, heart, lungs, confrontational visual fields (eyes), breast (optional), abdomen, external genitalia (optional), extremities, neurologic function, back, and lymph nodes. A targeted physical examination only includes the review of the following body systems: skin, heart, lungs, confrontational visual fields (eyes), abdomen, and examination of body systems where there are symptom complaints by the subject.
 
^h Subject will be evaluated to reveal any potential abnormalities in the following neurologic domains: vision, motor, tactile sensation, coordination/cerebellar function, speech, verbal comprehension, cognition/behavior.
 
ⁱ Vital signs (including blood pressure, pulse, respiratory rate, and temperature) and 12-lead ECG should be performed prior to collection of blood samples for laboratory assessments.
 
^j Contraception check should be performed for female subjects of childbearing potential and male subjects who are with a partner of childbearing potential.
 
^k For confirmation of postmenopausal status in females who have had 12 consecutive months of spontaneous amenorrhea and are ≥51 years of age. This does not need to be performed if postmenopausal status was confirmed by FSH in induction study SHP647-301 or SHP647-302. If a female subject's status has changed to postmenopausal since the induction studies (SHP647-301 or SHP647-302), the FSH confirmation test will be done at baseline (Visit 1) of SHP647-303. Once FSH results are received, and if postmenopausal status is uncertain, the routine pregnancy testing will continue as planned for the remainder of the study. If postmenopausal status is confirmed, routine pregnancy testing is no longer required.
 
^l For females of childbearing potential that are not surgically sterile, do not have confirmed ovarian failure, or do not meet the definition of postmenopausal.
																	

Study Week	Baseline ^a	Treatment												Follow-Up ^b			
	0	4	8	12	16	20	24	28	32	36	40	44	48	52 ^c		60 ^c	68 ^c
Visit Number	1	2	3	4	5	6	7	8	9	10	11	12	13	14 (Pt 1) ^d	14 (Pt 2)	15	16
Study Day	1	28	56	84	112	140	168	196	224	252	280	308	336		364	420	476
Visit Window	None	±7 days													±7 days	±7 days	

^m Samples must be collected before administration of investigational product.

ⁿ Flexible sigmoidoscopy or colonoscopy (if preferred). Biopsy samples will be collected for histological evaluation using the Geboes Score classification.

^o Mayo and PRO-UC assessments will be based on subject daily e-diary entries.

^p The total Mayo score at Week 52 (Visit 14, Part 2) will be calculated based on the centrally read endoscopic subscore for the endoscopy performed at Week 52 (Visit 14, Part 1).

^q PRO UC daily e-diary will be collected daily for 10 days before each visit. See Section for further details. Compliance is assessed by site staff at each visit. The site staff will instruct the subject on the appropriate use of the e-diary, particularly when compliance is below 80% (eg, <8 out of 10 diary entries) when compared with the previous visit.

^r All health outcome or patient-reported questionnaires should be completed before completing any other visit assessments.

^s Interactive response technology will be used for randomization and dispensation of study treatment.

^t Stool sample collection kit will be dispensed to the subject to take home at the visit prior to the visit at which testing will be done.

Study Week	Baseline ^a	Treatment													Follow-Up ^b	
	0	4	8	12	16	20	24	28	32	36	40	44	48	52/ET ^c		64 ^c
Visit Number	1	2	3	4	5	6	7	8	9	10	11	12	13	14 (Pt 1) ^d	14 (Pt 2) ^d	15
Study Day	1	28	56	84	112	140	168	196	224	252	280	308	336		364	448
Visit Window	None	±10 days													±10 days	±10 days
Treatment Procedures																
Randomization ^v	X															
Administration of ontamalimab or placebo ^{v,w,x}	X	X	X	X	X	X	X	X	X	X	X	X	X			
Hypersensitivity monitoring ^y	X	X	X	X	X	X	X	X	X	X	X	X	X	X	X	X
Adverse events	X	X	X	X	X	X	X	X	X	X	X	X	X	X	X	X
Concomitant medication and procedures	X	X	X	X	X	X	X	X	X	X	X	X	X	X	X	X
Dispense stool collection kit for stool sample ^z			X			X							X			

ADA=antidrug antibody; β-hCG=beta-human chorionic gonadotropin; ██████████; ECG=electrocardiogram; e-diary=electronic diary; ET=early termination; FSH=follicle-stimulating hormone; HEENT=head, eyes, ears, nose, and throat; IDT=induction study (SHP647-301 or SHP647-302); LTS=long-term safety extension; NAb=neutralizing antibody; PRO=patient-reported outcome; Pt=part; UC=ulcerative colitis

Note: As soon as Amendment 3 is implemented, the subject's next scheduled visit will be the ET visit, which should be conducted no later than 4 weeks (±10 days) from the subject's last study visit prior to the implementation of SHP647-304 Amendment 4.

- ^a The Week 12 assessment from the induction study (SHP647-301 or SHP647-302) will be used as the baseline (Day 1/Week 0) assessments for Study SHP647-303.
- ^b No follow-up is required if subject is entering the LTS study (SHP647-304) at the Week 52/ET visit (Visit 14).
- ^c Any subject who is prematurely withdrawn from the study (including for treatment failure) should return for the ET visit and then enter into the safety follow-up period if not entering the LTS study (SHP647-304). Subjects who enter the safety follow-up period will have a final visit at 12 weeks following the Week 52/ET visit. Both the Week 52/ET and 12-week safety follow-up visits are preferred to be on-site visits; however, due to the COVID-19 situation, these may also be done at a subject's home provided a qualified site staff member performs these evaluations following DTP guidance.
- ^d Part 1 of Visit 14 must be completed within 10 days (preferably, within 5 to 7 days) before Part 2; this will allow sufficient time for data from the centrally read endoscopy to be available at Part 2 of the visit. For subjects who meet the criteria for treatment failure (as defined in Protocol Section 4.5.1.1) or are discontinuing prior to completing the 52-week treatment period due to early study closure and will be entering the LTS study (SHP647-304), Part 2 of Visit 14 should be scheduled at least 2 weeks after the last dose of investigational product, to allow a sufficient time interval prior the first dose in the LTS study.
- ^e Eligibility will be assessed after the consent form is signed and after induction study SHP647-301 or SHP647-302 Week 12, Visit 6 (Part 2) procedures are completed.
- ^f Medical history for induction study SHP647-301 or SHP647-302 will be used as the baseline medical history data for Study SHP647-303.
- ^g Complete physical examination includes the review of the following body systems: general appearance, skin, HEENT, heart, lungs, confrontational visual fields (eyes), breast (optional), abdomen, external genitalia (optional), extremities, neurologic function, back, and lymphnodes. A targeted physical examination only includes the review of the following body systems: skin, heart, lungs, confrontational visual fields (eyes), abdomen, and examination of body systems where there are symptom complaints by the subject.

Study Week	Baseline ^a	Treatment												Follow-Up ^b		
	0	4	8	12	16	20	24	28	32	36	40	44	48	52/ET ^c	64 ^c	
Visit Number	1	2	3	4	5	6	7	8	9	10	11	12	13	14 (Pt 1) ^d	14 (Pt 2) ^d	15
Study Day	1	28	56	84	112	140	168	196	224	252	280	308	336		364	448
Visit Window	None	±10 days												±10 days	±10 days	

- ^h Subject will be evaluated to reveal any potential abnormalities in the following neurologic domains: vision, motor, tactile sensation, coordination/cerebellar function, speech, verbal comprehension, and cognition/behavior. See Section 7.2.3.3 of the protocol for further details.
- ⁱ In case of a DTP situation, to be performed by remote visits via virtual communications (eg, TeleHealth application).
- ^j Vital signs (including blood pressure, pulse, respiratory rate, and temperature) and 12-lead ECG should be performed prior to the collection of blood samples for laboratory assessments.
- ^k Contraception check should be performed for female subjects of childbearing potential and male subjects who are with a partner of childbearing potential. See Section 4.4 of the protocol for further details.
- ^l Clinical laboratory assays (LFT) can also be performed by the local laboratory in case of issues related to the COVID-19 pandemic and if deemed necessary by the investigator to confirm the subject's safety. In such a case, the investigative site must obtain the local laboratory's normal ranges as well as CLIA (Clinical Laboratory Improvement Amendments) certificate, and the investigator must add the local laboratory as appropriate.
- ^m Subjects performing home administrations consecutively for 3 months will need to perform LFT per FDA requirement. It may be done locally if it is not possible to collect samples at the central laboratory.
- ⁿ When a subject experiences an increase in gastrointestinal symptoms, which could be an exacerbation of disease, an infectious etiology must be evaluated including testing for *Clostridium difficile* as described in Appendix 4 of the protocol.
- ^o For confirmation of postmenopausal status in females who have had 12 consecutive months of spontaneous amenorrhea and are ≥51 years of age. This does not need to be performed if postmenopausal status was confirmed by FSH in induction study SHP647-301 or SHP647-302. If a female subject's status has changed to postmenopausal since the induction studies (SHP647-301 or SHP647-302), the FSH confirmation test will be done at baseline (Visit 1) of SHP647-303. Once FSH results are received, and if postmenopausal status is uncertain, the routine pregnancy testing will continue as planned for the remainder of the study. If postmenopausal status is confirmed, routine pregnancy testing is no longer required.
- ^p For females of childbearing potential that are not surgically sterile, do not have confirmed ovarian failure, or do not meet the definition of postmenopausal as described in Section 4.4.1 and Section 7.3.3.7 of the protocol.
- ^q Samples must be collected before administration of investigational product.
- ^r Flexible sigmoidoscopy or colonoscopy (if preferred). Biopsy samples will be collected for histological evaluation using the Geboes Score classification and [REDACTED]. Note: For subjects discontinued from the study under Amendment 3 and prior to the completion of 52 weeks of treatment, endoscopy is not required (optional) at the ET visit.
- ^s Mayo and PRO-UC assessments will be based on the subject's daily e-diary entries.
- ^t The total Mayo score at Week 52/ET (Visit 14, Part 2) will be calculated based on the centrally read endoscopic subscore for the endoscopy performed at Week 52 (Visit 14, Part 1).

Study Week	Baseline ^a	Treatment												Follow-Up ^b		
	0	4	8	12	16	20	24	28	32	36	40	44	48	52/ET ^c	64 ^c	
Visit Number	1	2	3	4	5	6	7	8	9	10	11	12	13	14 (Pt 1) ^d	14 (Pt 2) ^d	15
Study Day	1	28	56	84	112	140	168	196	224	252	280	308	336		364	448
Visit Window	None	±10 days												±10 days	±10 days	

^u PRO-UC daily e-diary will be available throughout the study. Subjects will be required to enter e-diary data daily. See Section 7.3.2.3 of the protocol for further details. Compliance is assessed by site staff at each visit. The site staff will instruct the subject on the appropriate use of the e-diary, particularly when compliance is below 80% (eg, <8 out of 10 diary entries) when compared with the previous visit.

^v All patient-reported questionnaires should be completed before completing any other visit assessments.

^w Interactive response technology will be used for randomization and dispensation of study treatment.

^x In a situation in which a subject is not able to visit the study site due to the COVID-19 public health emergency, DTP investigational product administration options may be available, in accordance with local regulations (refer to DTP guidance document).

^y At each visit, the subject will be assessed for the presence of Type I and Type III hypersensitivity reactions since the prior visit. If a suspected hypersensitivity reaction has occurred, the next dose of investigational product should be withheld if necessary until the precise etiology (investigational product related or not) has been determined. If a Type III reaction is suspected, appropriate samples for testing will be collected and stored until the adjudication committee determines whether testing is appropriate.

^z Stool sample collection kit will be dispensed to the subject to take home at the visit prior to the visit at which testing will be done.

Note: See Section 7.3 of the protocol for the order in which assessments should be performed. Timing of visits is relative to SHP647-303 baseline (Visit 1).

